7.3.2 Paternal exposure

Male patients should refrain from fathering a child or donating sperm during the study and for 16 weeks (5 half-lives) following the last dose.

Pregnancy of the patient's partners will not be considered an AE. However, the outcome of all pregnancies (spontaneous miscarriage, elective termination, ectopic pregnancy, normal birth, or congenital abnormality) should be followed up and documented for conceptions occurring from the date of the first administration of IP until 16 weeks (5 half-lives) after the last administration of IP.

8. EVALUATION AND CALCULATION OF VARIABLES

8.1 Statistical considerations

- All personnel involved with the analysis of the study will remain blinded until database lock
- Analyses will be performed by AstraZeneca or its representatives
- The SAP will be prepared prior to first patient randomized and any subsequent amendments will be documented, with final amendments completed prior to unblinding of the data

8.2 Sample size estimate

The study will have an estimated sample size of 50 patients in each treatment group. No formal statistical hypotheses will be tested. The sample size justification is based on the precision of the estimate of the GMTs (as $GMT_{vaccine} / GMT_{benralizumab+vaccine}$). With 50 patients per arm, the 90% CI for the GMT ratio would be 0.67 to 1.48, assuming an observed ratio of 1, and that the log (post-dose HAI antibody titer or post-dose MN antibody titer) is normally distributed with a standard deviation (SD) of 1.2 on the natural log scale (Langley et al 2013). No formal statistical hypotheses will be tested.

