The analysis of the anti-influenza antibody response endpoints—strain-specific GMFRs and GMTs—will be performed on the immunogenicity analysis set, defined as all randomized patients who received at least 1 dose of planned investigational product (ie, 1 dose of influenza vaccine plus 1 dose of benralizumab or placebo), had pre- and post-dose HAI antibody measurements, had pre- and post-dose MN antibody measurements, and had no protocol deviation judged to have the potential to interfere with the generation or interpretation of an humoral response to the influenza vaccine. GMFRs and GMTs will be summarized by treatment group, and the group ratio of GMFRs (influenza vaccine divided by benralizumab and influenza vaccine) and GMTs and their corresponding 90% confidence intervals (CIs) will be constructed.

The antibody response to the influenza vaccine is defined as a ≥4-fold rise in HAI from Week 8. The proportion of patients who experience a post-dose HAI antibody response at Week 12 and corresponding 90% Clopper-Pearson exact CI will be summarized by treatment group.

The proportion of patients who achieve a post-dose HAI antibody titer ≥40 at Week 12 and corresponding 90% Clopper-Pearson exact CI will be summarized by treatment group.

The proportion of patients who achieve a post-dose HAI antibody titer ≥320 at Week 12 and corresponding 90% Clopper-Pearson exact CI will be summarized by treatment group.

The antibody response to the influenza vaccine is also defined as a ≥4-fold rise in MN antibody from Week 8. The proportion of patients who experience a post-dose MN antibody response at Week 12 and corresponding 90% Clopper-Pearson exact CI will be summarized by treatment group.

For GMFR and GMT, the geometric least square mean ratio between treatment groups (placebo/benralizumab) will be calculated via an analysis of covariance (ANCOVA) model on the log-transformed variable, adjusting for treatment group. The least square geometric mean ratio will be provided with associated 90% CI.

No interim blinded review is planned.

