No formal statistical hypotheses will be tested. The sample size justification is based on the precision of the estimate of the GMTs (as $GMT_{vaccine} / GMT_{benralizumab+vaccine}$). With 50 patients per arm, the 90% CI for the GMT ratio would be 0.67 to 1.48, assuming an observed ratio of 1, and that the log (post-dose HAI antibody titer or post-dose MN antibody titer) is normally distributed with a standard deviation (SD) of 1.2 on the natural log scale (Langley et al 2013).

All safety parameters will be analyzed descriptively. Safety analyses will be based on the safety analysis set, defined as all patients who received at least 1 dose of investigational product.

TABLE OF CONTENTS **PAGE** TITLE PAGE LIST OF ABBREVIATIONS AND DEFINITION OF TERMS 12 1. 1.1 1.2 13 Benefit/risk and ethical assessment 17 1.4 Study design _______17 2. 2.1 Primary Objective. 20 2.2 23 Safety Objective _______21 PATIENT SELECTION, ENROLLMENT, DISCONTINUATION, AND 3. Inclusion criteria 21 3.1 3.2 Exclusion criteria 23 Patient enrolment and randomization. 25 33 3.4 3.5 3.5.1 3.5.1.1 Background medication 26 3.5.1.2 3.5.2 Restrictions 27 3.5.2.1 Asthma medication restrictions 27 3.5.2.2 Other medication restrictions 27 3.5.2.3 Other restrictions 28 36 Withdrawal from the study 29 3.7 3.7.1 Screen failures 29 3.7.2 3.8

4.	STUDY PLAN AND PROCEDURES	31
4.1 4.1.1 4.1.2 4.1.3 4.1.3.1	Enrollment and screening period Enrollment (Visit 1) Screening (Visit 2) Re-screening Procedures for patients who experience an exacerbation during screening/run-in	33
4.2	Randomized treatment period	34
4.3	Follow-up period	. 34
5.	STUDY ASSESSMENTS AND TIMING OF PROCEDURES	. 34
5.1 5.1.1 5.1.2 5.1.2.1	Efficacy assessments Humoral response to influenza vaccine. Spirometry Reversibility test and post-BD FEV ₁ assessment.	34
5.2 5.2.1 5.2.1.1 5.2.1.2 5.2.2 5.2.3 5.2.4 5.2.4.1	Safety assessments Physical examination Complete physical examination Brief physical examination Vital signs Local electrocardiogram Safety laboratory tests Pregnancy test	37 37 37 37 38

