3.3 Patient enrolment and randomization

Investigator(s) should keep a record of patients considered for and included in the study. This pre-screening/screening log will be evaluated periodically by AstraZeneca or its delegates during routine monitoring visits.

Each patient should meet all of the inclusion criteria and none of the exclusion criteria for this study. Under no circumstances can there be exceptions to this rule.

The Investigator will:

- 1. Obtain signed informed consent/assent as appropriate with local guidance from the potential patient before any study specific procedures are performed
- 2. Assign each potential patient a unique enrollment number beginning with E# via interactive web/voice response system (IWRS/IVRS)

- 3. Determine patient eligibility
- 4. Assign eligible patient unique randomization code via IWRS/IVRS

If a patient withdraws from participation in the study, then his/her enrolment/randomization code cannot be reused.

Patients will be allocated to treatment arms in a 1:1 ratio. Specific information concerning the use of the IWRS/IVRS will be provided in the separate manual. Randomized patients who discontinue from IP administration will not be replaced.

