3.6 Discontinuation from investigational product

Patients will be discontinued from IP in the following situations:

- 1. Patient decision. The patient is free to discontinue treatment at any time, without prejudice (see Section 3.7)
- 2. Adverse event (AE) that in the opinion of the Investigator or Sponsor contraindicates further dosing
- 3. Risk to patient as judged by the Investigator or AstraZeneca
- 4. Eligibility requirement found not to be fulfilled (see Section 3.4). Risk to patient as judged by the Investigator or AstraZeneca.
- 5. Severe non-compliance with study protocol
- 6. Pregnancy
- 7. Lost to follow-up¹
- 8. Development of any study specific criteria for discontinuation:

¹ Patient is considered lost to follow up when any of the following attempts of contact are failed: 3 attempts of either phone calls, faxes or emails; having sent one registered letter/certified mail; or one unsuccessful effort to check the vital status of the patient using publicly available sources, if allowed by local regulations.

- (a) Anaphylactic reaction to the investigational product requiring administration of epinephrine
- (b) Development of helminth parasitic infestations requiring hospitalization
- (c) An asthma-related event requiring mechanical ventilation

All patients who prematurely discontinue investigational product should return to the study center and complete the procedures described for the Premature IP Discontinuation (IPD) visit within 4 weeks ± 3 days.

The reasons for premature discontinuation of IP should be recorded in the eCRF.

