4. STUDY PLAN AND PROCEDURES

Table 1 Study Plan – Enrollment, screening period

		Screening			
	D.C.	V1	V2ª		
Assessment/ activity	Refer to	(W -4 to W -2)			
Informed consent/assent	10.4	X			
Inclusion/exclusion criteria	3.1/3.2	X	X		
Medical and asthma history b	4.1.1	X			
Complete physical examination	5.2.1.1	X			
Weight, Height, BMI	5.3.1	X			
Vital Signs	5.2.2	X	X		
Local ECG	5.2.3	X			
Serum chemistry	5.2.4	X			
Hematology	5.2.4	X			
Urinalysis	5.2.4	X			
Serum concentration (theophylline) ^c	3.5.2.2	X			
Serology (hepatitis B,C; HIV-1; HIV-2)	5.3.4.1	X			
Serum pregnancy test	5.2.4.1	X			
Pre-bronchodilator FEV ₁ d	5.1.2.1	X	X		
Post-bronchodilator FEV ₁ ^d	5.1.2.1	X	X		
Adverse events	7.1	X	X		
Concomitant medication	3.5	X	X		

Visit 1 and Visit 2 can be combined if the patient has the time and they have not taken SABAs for 6 hours or their long-acting bronchodilator-containing therapy for 12-24 hours. If spirometry/reversibility procedures are actually planned at Visit 1 as a convenience, then the ICF/assent must be signed prior to Visit 1 and prior to instructing the patient to withhold any medication.

To include influenza vaccination history.

For patients on the ophylline (see Section 3.5.2.2)

Pre- and post-bronchodilator spirometry can be done at Visit 1 OR Visit 2. If patients do not demonstrate airway reversibility at either Visit 1 or Visit 2 and this is needed to qualify the patient for randomisation, the site should screen fail the patient.

BMI Body mass index; D Days; ECG Electrocardiogram; HIV Human immunodeficiency virus; V Visit; W Week.

Table 2 Study Plan – Randomization, treatment period, and follow-up

	Refer to	Treatment			ARE/EOT	IPD	FU	Unsch
		V3	V4	V5	V6		V7	
Assessment/ activity		W0	W4	W8	W12		W20	
			Visit window (days) ^a					
		±0	±3	±3	±3	±3	±3	
Inclusion/exclusion criteria	3.1/3.2	X						
Randomization	3.3	X						
Administration of investigational product ^c	6.8	X	X	X				
Administration of influenza vaccine ^e				X				
Complete physical examination	5.2.1.1	X			X	X	X	
Brief physical examination	5.2.1.2		X	X				X
Vital Signs	5.2.2	X	X	X	X	X	X	X
ACQ-6	5.3.3	X	X	X	X	X		
Asthma exacerbation assessment	5.3.2	X	X	X	X	X	X	X
Adverse events	7.1	X	X	X	X	X	X	X
Concomitant medication	3.5	X	X	X	X	X	X	X
Serum chemistry	5.2.4	X			X	X	X	
Hematology	5.2.4	X			X	X	X	
Urinalysis	5.2.4	X			X	X	X	
Urine pregnancy test (dipstick) b	5.2.4.1	X	X	X	X	X	X	
PK	5.3.5	X		X	X	X	X	
ADA	5.3.7	X		X	X	X	X	

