8.3 Definitions of analysis sets

Antibody endpoints to the influenza vaccine—strain-specific HAI and MN antibody GMFRs and GMTs—will be analyzed using the vaccine immunogenicity analysis set. All remaining efficacy analyses will be performed using an Intent-to-Treat (ITT) approach based on the full analysis set. For consistency, demographic and baseline characteristics will be presented using the full analysis set. Safety objectives and ADA will be analyzed based on the Safety analysis set.

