8.3.3 Vaccine immunogenicity analysis set

The vaccine immunogenicity analysis set will include all randomized subjects who received at least 1 dose of planned IP (ie, 1 dose of influenza vaccine, and plus 1 dose of benralizumab or placebo), had pre- and post-dose HAI and MN antibody measurements, and had no protocol deviation judged to have the potential to interfere with the generation or interpretation of an antibody response. The analyses conducted using this analysis set will be based on the actual treatment received. Protocol deviations will be reviewed by the study team before unblinding.

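### The precision statement behind the sample size counts every randomized patient as analyzed, and the HAI analysis needlessly depends on MN results

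*Protocol*

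**What the plan says.** Section 8.2 states that no formal hypothesis is tested and that the sample size rests on the precision of the GMT ratio: "With 50 patients per arm, the 90% CI for the GMT ratio would be 0.67 to 1.48, assuming an observed ratio of 1". It assumes an SD of 1.2 on the natural log scale. The synopsis gives the same interval.

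Fifty per arm is the enrolment target. The synopsis plans to randomize about 100 patients, and Figure 1 shows 100 subjects allocated 1:1, 50 to each arm. Section 3.3 adds: "Randomized patients who discontinue from IP administration will not be replaced".

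GMTs and geometric mean fold rises (GMFRs) are not analyzed in all randomized patients. Sections 8.3 and 8.5.1 assign them to the vaccine immunogenicity analysis set. Under section 8.3.3, members of that set must have received the influenza vaccine and at least one dose of benralizumab or placebo, and must have "had pre- and post-dose HAI and MN antibody measurements, and had no protocol deviation judged to have the potential to interfere". The synopsis has the same two-assay condition: "had pre- and post-dose HAI antibody measurements, had pre- and post-dose MN antibody measurements". For the other efficacy endpoints, section 8.3 says: "All remaining efficacy analyses will be performed using an Intent-to-Treat (ITT) approach based on the full analysis set".

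**The concern.** The interval is computed on one population and the estimate on a smaller one. A patient can be randomized and still not contribute to the GMT ratio in three ways: leaving before the Week 8 vaccination, missing the Week 12 sample, or having a deviation judged to interfere with the antibody response. The schedule itself creates the first route. Under section 3.6, patients who stop study treatment early "should return to the study center and complete the procedures described for the Premature IP Discontinuation (IPD) visit", but the Table 2 row "Administration of influenza vaccine" is marked only at Visit 5. Appendix G restricts influenza vaccination at any other time during the study. Sections 8.2 and 3.3 contain neither an attrition allowance nor replacement.

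The second problem is the joint assay rule. HAI endpoints are primary (section 2.1) and MN endpoints secondary (section 2.2). With one set requiring both pairs, a patient whose HAI titers are complete but whose MN result is missing leaves the HAI GMT and HAI GMFR analyses. The other two primary endpoints, the proportions with a 4-fold HAI rise and with HAI titer of at least 40, are not affected on the text of section 8.3, because they fall to the full analysis set.

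At stake is the accuracy of the only figure offered in support of the sample size, and the loss of usable primary data for a reason unrelated to the primary assay.

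**Working it through.** **Inputs from the protocol.** SD 1.2 on the natural log scale, observed ratio 1 and 50 per arm (section 8.2); two-sided 90% interval (sections 8.2 and 8.5.1); 1:1 allocation (section 3.3).

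**Inputs assumed.** The proportion not evaluable. The protocol gives none, so 10%, 20% and 30% are shown. The number with only an MN result missing is also assumed, at 2 per arm.

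**Formula.** With n analyzed patients per arm, the half-width on the log scale is h = 1.645 × 1.2 × √(2/n), and the interval at a ratio of 1 is exp(−h) to exp(+h).

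**The protocol's own figure.** n = 50: h = 1.645 × 1.2 × √(2/50) = 1.645 × 1.2 × 0.2 = 0.3948, which gives 0.674 to 1.484. This matches 0.67 to 1.48. A t quantile on 98 degrees of freedom would give 0.671 to 1.490, so the protocol used the normal quantile with n equal to the number analyzed.

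**The same formula at evaluable numbers.** The half-width relative to n = 50 is √(50/n).

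| Analyzed per arm | Assumed loss | h | 90% CI | Half-width relative to n = 50 |
|---|---|---|---|---|
| 50 | 0% | 0.3948 | 0.67 to 1.48 | 1.00 |
| 45 | 10% | 0.4161 | 0.66 to 1.52 | 1.05 |
| 40 | 20% | 0.4414 | 0.64 to 1.55 | 1.12 |
| 35 | 30% | 0.4718 | 0.62 to 1.60 | 1.20 |

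**Joint assay rule.** Suppose 45 per arm have valid HAI pairs and meet every other condition, and 2 of them lack only an MN result. HAI is then analyzed at 45 − 2 = 43 per arm: h = 1.645 × 1.2 × √(2/43) = 0.4257, or 0.65 to 1.53, instead of 0.66 to 1.52 at 45.

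**The case against.** The strongest reply is that section 8.2 is conditional and true as written: with 50 patients per arm the interval is what it says. There is no margin, power or precision target, so nothing fails at 45 or 40 per arm, and the planned sizes are described as approximate or estimated. The shift is also within the uncertainty of the planning SD. At 50 per arm an SD of 1.3 gives h = 1.645 × 1.3 × 0.2 = 0.4277, or 0.65 to 1.53, about the same as 43 per arm at an SD of 1.2. At 5% loss (about 47 per arm) the interval is 0.67 to 1.50, hardly different. Stopping study treatment does not by itself exclude anyone: one dose is enough, and at Week 8 the vaccine is given before the study injection (section 6.8), so only those who stop before Visit 5 miss it. That they miss it is inferred from the schedule, since no sentence forbids vaccinating them. Finally, a common set gives HAI and MN results on the same patients, which is a legitimate choice.

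Much of this stands: the effect is small, the loss rates are assumptions, and no decision rule changes. It does not answer the main point. Describing the enrolment number as approximate allows for error in either direction, whereas entry into a restricted set can only reduce the number. On the assay rule, matched denominators are a convenience. The protocol gives no reason to pay for them with primary HAI data, although the price is probably low because both assays are tested at the same two visits (section 5.1.1).

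**Conclusion.** The concern holds. The stated interval is correct for 50 analyzed patients per arm, but it describes a trial in which no randomized patient is lost from the immunogenicity set, and the protocol neither plans for nor claims that. With an assumed 10% to 20% loss, the upper limit moves from 1.48 to between 1.52 and 1.55 and the log-scale half-width grows by 5% to 12%. These figures rest on the protocol's SD of 1.2, a ratio of 1, equal loss in both arms and the assumed rates. The overstatement is modest and invalidates no conclusion, but precision is the sole stated basis for the sample size, so the figure should describe the patients who will be analyzed.

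The joint assay rule is a smaller, separate defect. It can remove valid HAI pairs from two of the four primary endpoints because of a secondary assay. This is probably rare, and it can be avoided.

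**What to change.** 1. In section 8.2 and the synopsis, state the precision at an expected evaluable number. For example: *Of 50 patients randomized to each arm, about 45 are expected in the vaccine immunogenicity analysis set, on the assumption that 10% are not evaluable. At an observed GMT ratio of 1 and an SD of 1.2, the 90% CI would then run from 0.66 to 1.52; with 20% not evaluable it would run from 0.64 to 1.55.* The sponsor should replace the 10% with its own expected rate if it has one. No added enrolment is needed.
2. In section 8.3.3 and the synopsis, make the titer condition assay-specific: pre- and post-dose HAI results for HAI GMT and GMFR, and pre- and post-dose MN results for MN GMT and GMFR. The other conditions for the set can stay as they are.
3. While editing, reconcile section 8.3.3 with section 8.5. Section 8.5 includes all efficacy data whatever the protocol adherence, whereas section 8.3.3 excludes patients for interfering deviations. The choice affects how many patients are expected to be evaluable.

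The cost is wording only. The stated interval becomes slightly wider, and the HAI and MN denominators may differ by a few patients.

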8.3 Definitions of analysis sets

Antibody endpoints to the influenza vaccine—strain-specific HAI and MN antibody GMFRs and GMTs—will be analyzed using the vaccine immunogenicity analysis set. All remaining efficacy analyses will be performed using an Intent-to-Treat (ITT) approach based on the full analysis set. For consistency, demographic and baseline characteristics will be presented using the full analysis set. Safety objectives and ADA will be analyzed based on the Safety analysis set.

8.3.1 All patients analysis set

This analysis set will comprise all patients screened for the study and will be used for reporting of disposition and screening failures.

8.3.2 Full analysis set

All patients randomized and receiving any IP will be included in the full analysis set, irrespective of their protocol adherence and continued participation in the study. Patients will be analyzed according to their randomized treatment, irrespective of whether or not they have prematurely discontinued, according to the ITT principle. Patients who withdraw consent to participate in the study will be included up to the date of their study termination.

8.3.3 Vaccine immunogenicity analysis set

The vaccine immunogenicity analysis set will include all randomized subjects who received at least 1 dose of planned IP (ie, 1 dose of influenza vaccine, and plus 1 dose of benralizumab or placebo), had pre- and post-dose HAI and MN antibody measurements, and had no protocol deviation judged to have the potential to interfere with the generation or interpretation of an antibody response. The analyses conducted using this analysis set will be based on the actual treatment received. Protocol deviations will be reviewed by the study team before unblinding.

8.3.4 Safety analysis set

All patients who received at least 1 dose of IP will be included in the safety analysis set. Patients will be classified according to the treatment they actually received. A patient who has on one or several occasions received active treatment will be classified as active. All safety and ADA summaries will be based on this analysis set.

8.3.5 Pharmacokinetic analysis set

All patients who received benralizumab and from whom PK blood samples were obtained are assumed not to be affected by factors such as protocol violations. Those patients who had at least 1 quantifiable serum PK observation post first dose will be included in the PK analysis dataset. All PK summaries will be based on this analysis set.

8.4 Variables for analyses

8.4.1 Calculation or derivation of efficacy variables

All efficacy objectives will be evaluated for the double-blind treatment period, defined as the period after administration of randomized IP at Week 0 and the conclusion of Week 12 (EOT) visit, inclusive.

8.4.1.1 Humoral immune response following seasonal influenza virus vaccination

The benralizumab versus placebo humoral immune responses following seasonal influenza virus vaccination will be assessed by

Primary objective:

- Post-dose strain-specific HAI antibody geometric mean folder rises (GMFRs) from Week 8
- Post-dose strain-specific HAI antibody geometric mean titers (GMTs) obtained at Week 12
- Proportion of patients who experience a strain-specific post-dose antibody response at Week 12 with antibody response defined as a ≥4-fold rise in HAI antibody titer from Week 8
- Proportion of patients who achieve a strain-specific post-dose HAI antibody titer ≥40 at Week 12

Secondary objectives:

- Proportion of patients who achieve a strain-specific post-dose HAI antibody titer ≥320 at Week 12
- Post-dose strain-specific microneutralization (MN) antibody GMFRs from Week 8
- Post-dose strain-specific serum MN antibody GMTs obtained at Week 12
- Proportion of patients who experience a strain-specific post-dose antibody response at Week 12 with antibody response defined as a ≥4-fold rise in MN antibody titer from Week 8

